10.2 Subsequent cycles (all patients)

In summary treatment should be delayed for any patient experiencing:

- Grade 4 thrombocytopenia with active bleeding
Grade 4 anaemia and Grade 4 thrombocytopenia (without active bleeding) do not require the Carfilzomib dose to be withheld. Participants should receive supportive measures in accordance with institutional guidelines.
- Grade 4 neutropenia or neutropenic fever
- Grade 3/4 non-haematological toxicity

Treatment should continue to be withheld until the neutrophil count and platelet count return to $\geq 0.75 \times 10^9/L$ and $\geq 25 \times 10^9/L$, respectively (during a cycle). Drug-induced non-haematological toxicities have to have reached baseline, or become Grade ≤ 1 prior to re-treatment. Treatment may be delayed up to 8 days to allow sufficient time for recovery from toxicities. Please check table 3 and table 5 for dose reduction guidelines.

If the haematological or non-haematological AE has not resolved within 14 days the patient must discontinue from therapy, if the haematological or non-haematological toxicities have resolved within 14 days, the patient may have their therapy re-instituted at the next lowest dose level. Please check table 3 and table 5 for dose reduction guidelines.

A dose delay of up to 14 days (up to 3 weeks for infection treatment) is permitted at the beginning of a cycle to allow resolution of toxicity. If there is no resolution of toxicity as stated above after 2 weeks of withholding treatment (3 weeks for infection treatment), the participant will be discontinued from treatment. Withholding treatment for more than 2 weeks for other reasons, eg elective surgery such as vertebroplasty, may be permitted after discussion with the CI.

No more than three dose reductions or delays in two consecutive cycles will be permitted in an individual participant on study. If toxicity continues or recurs after three dose reductions or delays, the participant should be discontinued from treatment.

If a patient vomits after taking a dose of an oral agent, no repeat dose should be taken and patient will continue as per schedule but the clinical team should consider prophylactic antiemetics.

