10.4 Dose Reduction For Haematologic Toxicities

Patients will have a FBC prior to each dose of Carfilzomib during treatment.

Carfilzomib will be withheld from participants with:

- Grade 4 thrombocytopenia with active bleeding
- Grade 4 neutropenia

The following table outlines the dose reduction guidelines for Carfilzomib for thrombocytopenia and neutropenia:

Table 3: Recommended Action for Haematologic Toxicities

Haematologic Toxicity	Recommended Action	
Thrombocytopenia		
When platelets fall to $\leq 25 \times 10^9 / L$	If platelets $10 - 25 \times 10^9 / L$ without evidence of bleeding	Continue at same dose
	If evidence of bleeding or platelets $< 10 \times 10^9 / L$	Withhold dose until platelets return to $\geq 10 \times 10^9 / L$ and/or bleeding is controlled, then resume at same dose.
For each subsequent drop to $\leq 25 \times 10^9 / L$	If platelets $10 - 25 \times 10^9 / L$ without evidence of bleeding	Continue at same dose
	If evidence of bleeding or platelets $< 10 \times 10^9 / L$	Withhold dose until platelets return to $\geq 10 \times 10^9 / L$ and/or bleeding is controlled, then resume at 1 dose decrement
Neutropenia		
When ANC falls to $\leq 0.75 \times 10^9 / L$	If ANC $0.5-0.75 \times 10^9 / L$	Continue at same dose

	If ANC $< 0.5 \times 10^9 / L$	Withhold dose until ANC returns to $\geq 0.5 \times 10^9 / L$, then resume at same dose.
For each subsequent drop to $\leq 0.75 \times 10^9 / L$	If ANC $0.5-0.75 \times 10^9 / L$	Continue at same dose
	If ANC $< 0.5 \times 10^9 / L$	Withhold dose until ANC returns to $\geq 0.5 \times 10^9 / L$, then resume at 1 dose decrement.
Neutropenic fever	If $< 1000/mm^3$ and single temperature $> 38.3^{\circ}C$ OR temperature $> 38.0^{\circ}C$ for more than one hour.	Withhold dose until ANC returns to baseline grade, then resume at same dose.

Please note; if doses of carfilzomib need to be delayed then the dexamethasone dose must also be delayed so that it can be taken prior to the carfilzomib dose. Thalidomide can be taken continuously unless there is toxicity directly attributable to Thalidomide.

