10.5 Dose Reductions for Non-Haematologic Toxicities

Carfilzomib should be withheld for events \geq Grade 3 until resolved to \leq Grade 1 or return to baseline.

After resolution of the event to \leq Grade 1 or return to baseline, if the adverse event was not treatment-related, subsequent treatment with Carfilzomib may resume at full dose. If the event was treatment-related, subsequent treatment with Carfilzomib will resume at one level dose reduction except for nausea, vomiting or diarrhoea which can be attributed to Carfilzomib (see table 5 below). If toxicity continues or recurs, a 2nd Carfilzomib dose reduction may be permitted at the discretion of the investigator. No more than three dose reductions will be permitted in an individual participant on study. If toxicity continues or recurs after three dose reductions, the participant should be discontinued from treatment.

Dose reduction guide for Carfilzomib:

Table 4: Dose Reduction Guide for Carfilzomib Dosing

Current dose	Reduce to
27mg/m ²	20mg/m ²
36 mg/m ²	27 mg/m ²
45 mg/m ²	36 mg/m ²
56 mg/m ²	45 mg/m ²

If the participant tolerates the reduced dose for two cycles, participant may be dose escalated to the dose prior to reduction following discussion with the CI and CTRU.

Dose adjustment guidelines for non-haematologic toxicities are summarised as follows:

Table 5: Dose Adjustment Guidelines for Non-Haematological Toxicities.

Symptom	Recommended Action Carfilzomib
Allergic reaction/hypersensitivity Grade 2 – 3 Grade 4	Withhold until \leq Grade 1, reinstitute at full dose. Discontinue (refer to section 14)
Tumour lysis syndrome (≥ 3 of following: $\geq 50\%$ increase in creatinine, uric acid, or phosphate; $\geq 30\%$ increase in potassium; $\geq 20\%$ decrease in calcium; or ≥ 2 -fold increase in LDH)	Withhold Carfilzomib until all abnormalities in serum chemistries have resolved. Reinstitute at full doses.

Infection Grade 3 or 4	Withhold Carfilzomib until systemic treatment for infection complete and infection resolves. If no neutropenia, restart at same dose. If neutropenic, follow neutropenia instructions.
Herpes zoster of any grade	Withhold Carfilzomib until lesions are dry. Reinstigate at full dose
Grade 3 Nausea or vomiting despite maximal anti-emetic therapy or diarrhoea	Withhold Carfilzomib until this resolves and re-start at full dose. If recurrent, re-start at one dose level lower

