10.9 Infections

Participants with active or suspected infections of grade III or greater should have treatment withheld until infection has resolved and anti-infective treatment has been completed. After the infection has resolved and anti-infective treatment has been completed, treatment may continue at the original dose. If there is no resolution of toxicity to ≤ Grade 1 or baseline after 3 weeks, the participant will be discontinued from treatment (see section 14).

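### Section 10.2's restart and 14-day stopping sentence does not match Tables 3 and 5 and section 10.9 for several of its own hold triggers

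*Protocol*

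**What the plan says.** Protocol section 10.2 covers toxicity in cycles after the first. It presents itself as a summary and lists the hold triggers: grade 4 thrombocytopenia with active bleeding, grade 4 neutropenia or neutropenic fever, and grade 3 or 4 non-haematological toxicity. One sentence then sets two outcomes. An event still unresolved at 14 days means that the patient must discontinue. If it has resolved by then, "the patient may have their therapy re-instituted at the next lowest dose level". The sentence makes no exception for a first event or for type of event. The next sentence reads "Please check table 3 and table 5 for dose reduction guidelines". The section closes by saying that toxicities other than neuropathic pain and sensory neuropathy are to be managed by Tables 3 and 5.

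The event-specific text reads differently:

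- Table 3 (section 10.4), neutropenic fever: "Withhold dose until ANC returns to baseline grade, then resume at same dose". A first neutrophil count below 0.5 and a first bleeding thrombocytopenia also resume at the same dose.
- Table 5 (section 10.5), hypersensitivity of grade 2 or 3: hold, then "reinstitute at full dose". Infection of grade 3 or 4: "If no neutropenia, restart at same dose".
- Section 10.9, infection of grade 3 or greater: "After the infection has resolved and anti-infective treatment has been completed, treatment may continue at the original dose". The stopping rule there applies to infection unresolved "after 3 weeks, the participant will be discontinued from treatment".
- The next paragraph of 10.2, on delays at the start of a cycle, also has the longer limit: "3 weeks for infection treatment), the participant will be discontinued from treatment".

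**The concern.** For the same event, a site that applies the 10.2 sentence as written gives one dose level less than a site that follows the table row. For a slow-resolving infection, one text stops treatment while the other allows a restart at the original dose.

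What is at stake is consistent dosing and the feasibility summaries in protocol section 19.4 and SAP section 5.3.2 (secondary endpoints): dose reductions and their reasons, withdrawals from treatment and time on treatment, together with relative dose intensity. An unneeded reduction also uses up one of the three that section 10.5 allows, and Table 4 lists no step below 20 mg/m².

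**Working it through.** **1. Event by event.** Each row is a 10.2 hold trigger.

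| Event | 10.2 sentence | Specific text |
|---|---|---|
| First ANC below 0.5 | One level lower | Table 3: same dose; decrement only from the next drop |
| First thrombocytopenia with bleeding | One level lower | Table 3: same dose; decrement only from the next drop |
| Neutropenic fever | One level lower | Table 3: same dose |
| Grade 3 hypersensitivity | One level lower | Table 5: full dose |
| Grade 3 or 4 infection, no neutropenia | One level lower | Table 5: same dose; 10.9: original dose |
| Infection unresolved at 14 days | Discontinue | 10.9: three weeks; 10.2, start of a cycle: three weeks |

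The sentence agrees with the tables for other events: repeat ANC below 0.5, repeat bleeding thrombocytopenia, grade 3 or higher liver-test elevation, renal dysfunction attributable to carfilzomib, and other carfilzomib-related events of grade 3 or higher. It is therefore wrong for some triggers, not all.

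**2. Size of one step (Table 4).** Step = 1 − lower/current.

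- 56 to 45: 11/56 = 19.6%
- 45 to 36: 9/45 = 20.0%
- 36 to 27: 9/36 = 25.0%
- 27 to 20: 7/27 = 25.9%

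**3. Cumulative dose over six full cycles.** There are 18 doses, the first at 20 mg/m², so planned dose = 20 + 17d. This gives 972, 785, 632 and 479 mg/m² for d = 56, 45, 36 and 27. Shortfall = (doses affected × step in mg/m²) / planned dose.

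| First event | Doses affected | d = 56 | d = 45 | d = 36 | d = 27 |
|---|---|---|---|---|---|
| Cycle 6 day 8 | 2 | 22/972 = 2.3% | 18/785 = 2.3% | 18/632 = 2.8% | 14/479 = 2.9% |
| Cycle 4 day 8 | 8 | 88/972 = 9.1% | 72/785 = 9.2% | 72/632 = 11.4% | 56/479 = 11.7% |
| Cycle 2 day 8, never re-escalated | 14 | 154/972 = 15.8% | 126/785 = 16.1% | 126/632 = 19.9% | 98/479 = 20.5% |

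The last row is near worst case. Six cycles is a maximum, and section 9.4 takes non-responders off trial treatment after three. Section 10.5 also allows re-escalation after two tolerated cycles. With re-escalation at cycle 5, about 8 doses are affected (2 + 3 + 3), which gives 9.1% to 11.7%.

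**4. How many patients might meet a trigger.** Take 26 at the recommended dose: the minimum of 6 from escalation plus 20 in expansion.

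- Febrile neutropenia at 1.1% (section 2.1.3.3, single agent in myeloma): 26 × 0.011 = 0.3 patients.
- Grade 3 or higher pneumonia in 1 of 11 (section 2.1.3.4, twice-weekly carfilzomib in AL amyloidosis, any cause): 26/11 = 2.4 patients. The exact 95% interval for 1/11 is 0.2% to 41.3%. That section gives 11 as evaluable for drug-related events, but its cohorts sum to 12; 1 of 12 gives 2.2.

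These are counts of triggering events, not of altered doses. Carrying the rates over to weekly carfilzomib with thalidomide and dexamethasone is an assumption.

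**5. Primary endpoints.** Dose-limiting toxicity is assessed up to the first dose of cycle 2, and cycle 1 of escalation has its own rule in section 10.1, so the maximum tolerated dose is untouched. The other primary endpoint is any grade 3 or 4 toxicity in any cycle. Every 10.2 trigger is already grade 3 or 4; neutropenic fever requires a count below 1000/mm³, which is at least grade 3 in Appendix 5. The patient counts as having the event before a restart dose is chosen. The by-cycle breakdown could shift in principle, but the documents give no basis for sizing that.

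**The case against.** The strongest reply is that the protocol already says which text prevails. Section 10.2 is a summary, the sentence says only that therapy may restart lower, a pointer to Tables 3 and 5 follows at once, and the section ends by making those tables the rule. A site that reduced after a first ANC below 0.5 would have to ignore adjacent instructions, and the documents give no rate at which that would happen. This stands, and it is why the point is minor. A reader might infer that 10.2 orders a reduction after every resolved toxicity; the permissive wording and the pointers do not support that.

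The reply does not dispose of the point. The lower level is the only restart dose that the sentence names. Section 10.1 uses almost the same words for dose-limiting toxicities, where a reduction is plainly meant, and section 10.9 uses the same permissive verb for restarting at the original dose, so the verb does not settle which text wins. The pointer is to guidance on reductions and could be read as giving the size of the step.

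A second reply is that the sentence follows an 8-day delay rule and so may cover only recoveries taking 8 to 14 days. The text does not say so. The difference would remain in any case, because for these events the table rows put no time limit on a same-dose or full-dose restart.

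A third reply is that the longer limit for infection is in the text twice, so its omission here adds little. But the stopping half of the sentence is mandatory, and the three-week allowance in 10.2 applies only at the start of a cycle. An infection resolving on day 17 within a cycle means discontinuation under one text and a restart under 10.9.

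**Conclusion.** A minor inconsistency, established from the text. For at least five kinds of hold trigger the restart dose named in 10.2 differs from the governing text, and for infection the stopping limit differs too (14 days against three weeks).

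The consequence, where a site follows the sentence over the tables, is one unneeded step of 19.6% to 25.9%, or early discontinuation for infection. The cumulative shortfall runs from about 2% for a late event to about 20% for an early event that is never re-escalated. On the assumed rates, roughly 0.3 to 2.4 of 26 patients would meet one of the two triggers that could be counted; how many would then be dosed or stopped differently cannot be derived from the documents.

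Relative dose intensity, dose-reduction counts and withdrawal counts could be affected. A reader might infer that the dose-finding result or the grade 3 or 4 primary endpoint is compromised; the documents do not support that, for the reasons in step 5 of the working. All analyses are descriptive, and section 11.2 records dose alterations and reasons each cycle, so divergence would be visible, though not prevented.

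**What to change.** In the 10.2 sentence, replace the phrase naming the next lower level with: *at the dose given in Table 3 (haematological), or in Table 5 and sections 10.5 (events not related to treatment), 10.9 (infection) and 10.10 (cardiac events) (non-haematological)*. Write the limit as *14 days (3 weeks for infection)*.

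The three sections are needed because Table 5 does not fully contain their restart rules. Section 10.5 is best cited only for unrelated events: its general text reduces all related events except nausea, vomiting and diarrhoea, which would bring back the mismatch with the Table 5 rows.

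The pointer should govern dose only. The recovery counts in 10.2 (ANC 0.75, platelets 25) differ from those in Table 3 (0.5 and 10), and this edit should leave them unchanged.

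Cost: one sentence in the next protocol amendment and a note to sites. No change to the sample size, endpoints or SAP.

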All previously established or new toxicities observed at any time, with the exception of neuropathic pain and peripheral sensory neuropathy, are to be managed as detailed in table 3 recommended action for haematologic toxicities and table 5 dose adjustment guidelines for non-haematological toxicities.

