Grade 2 treatment emergent neuropathy with pain or Grade 3 neuropathy	Continue to dose. If neuropathy persists for more than two weeks hold Carfilzomib until resolved to \leq Gr 2 without pain. Then restart at 1 dose decrement
\geq Grade 3 elevation in LFTs (AST, ALT, or total bilirubin)	Withhold dose. Resume at 1 dose decrement when toxicity has resolved to baseline.
Grade 4 neuropathy	Discontinue (refer to section 14)
Renal Dysfunction Serum creatinine equal to or greater than 2 x baseline, or CrCl $<$ 15mL/min (or CrCl decreases to \leq 50% of baseline) or need for dialysis.	Withhold dose and continue monitoring renal function (serum creatinine or serum creatinine clearance). If attributable to Carfilzomib, resume when renal function has recovered to within 25% of baseline. Start at 1 dose level reduction. If not attributable to Carfilzomib, dosing may be resumed at the discretion of the physician. If tolerated, the reduced dose may be escalated to the previous dose at the discretion of the physician. For patients on dialysis during Carfilzomib, the dose is to be administered after the dialysis procedure.
Congestive heart failure and other cardiopulmonary disorders.	See section 10.10. Any participant with marked worsening of symptoms of congestive heart failure, whether or not drug related, must have the dose withheld until resolution or return to baseline, after which treatment may continue at a reduced dose, or the subject may be permanently discontinued
Other non-haematologic toxicity assessed as Carfilzomib-related \geq Grade 3	Withhold dose until toxicity resolves to \leq Grade 2 or baseline. Restart at 1 dose decrement. If tolerated, the reduced dose may be escalated to the previous dose at the discretion of the physician.
PRES (posterior reversible encephalopathy syndrome with symptoms including headaches, altered mental status, seizures, visual loss, and hypertension).	If PRES suspected, withhold Carfilzomib. Consider evaluation with neuroradiological imaging for onset of visual or neurological symptoms suggestive of PRES. If PRES diagnosis is excluded, Carfilzomib administration may resume if clinically appropriate.

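### Section 10.2 excepts neuropathic pain and sensory neuropathy from Table 5, which holds the only neuropathy-specific carfilzomib rules; separately, two Table 5 rows restart at a grade the text does not allow

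*Protocol*

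**What the plan says.** Three places in the Protocol bear on this.

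- **Section 10.2, general rules.** Treatment is delayed for "Grade 3/4 non-haematological toxicity". Re-treatment needs recovery to baseline or grade 1 or less. An event not resolved within 14 days leads to discontinuation; one that has resolved in that time may restart at the next lower dose level. The next paragraph allows a delay at the start of a cycle and discontinues after two weeks of withholding (three for infection). The section closes by sending all toxicities to the tables, "with the exception of neuropathic pain and peripheral sensory neuropathy, are to be managed as detailed in table 3" and, as the sentence goes on, Table 5.
- **Section 10.5, text.** Carfilzomib is withheld for grade 3 or higher until grade 1 or less, or baseline. If the event was treatment-related, dosing resumes one level lower.
- **Section 10.5, Table 5.** One row covers "Grade 2 treatment emergent neuropathy with pain or Grade 3 neuropathy". Its action is "Continue to dose. If neuropathy persists for more than two weeks hold Carfilzomib until resolved to" at most "Gr 2 without pain. Then restart at 1 dose decrement". A second row, "Grade 4 neuropathy", discontinues. The catch-all row, "Other non-haematologic toxicity assessed as Carfilzomib-related" of grade 3 or more, withholds until at most "Grade 2 or baseline. Restart at 1 dose decrement".

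**The concern.** The excepted toxicities are the ones for which Table 5 has dedicated rows, and the sentence that excepts them points nowhere else. At the onset of grade 3 sensory neuropathy, one clinician could withhold carfilzomib under the general text and another continue it under Table 5, each with protocol wording in support.

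The restart mismatch comes later in an event and does not depend on the exception. A patient who started below grade 2 and whose event settles at grade 2 may restart under either of two Table 5 rows, but has not recovered under Sections 10.2 and 10.5 and would be discontinued once the time limit passes. The stake is inconsistent handling of individual patients.

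**Working it through.** **Step 1: is there another neuropathy rule?** Section 10.7 reduces or stops thalidomide for grade 3/4 toxicity attributable to thalidomide, and says nothing about carfilzomib. Section 10.11 lists cases in which carfilzomib need not be withheld; neuropathy is not among them. Section 10.12 gives no neuropathy rule, and Appendix 5 only grades it. The count is two rows in Table 5 and none elsewhere.

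**Step 2: the two readings, grade by grade.**

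| Sensory neuropathy | Exception taken literally (10.2 and 10.5 text) | Table 5 |
|---|---|---|
| Grade 2 with pain | No required carfilzomib action | Continue; hold if longer than two weeks |
| Grade 3 | Delay or withhold at once | Continue; hold if longer than two weeks |
| Grade 4 | May restart one level lower if resolved within 14 days | Discontinue |

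The general text is stricter at grade 3 and looser at painful grade 2 and grade 4, so neither reading is the safer default throughout. The grade 4 case is unlikely in practice, because Appendix 5 defines grade 4 as life-threatening. Motor neuropathy is outside the exception.

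**Step 3: restart thresholds.**

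- 10.2 and 10.5 text: grade 1 or less, or baseline.
- Table 5, neuropathy row: grade 2 or less without pain.
- Table 5, catch-all row: grade 2 or less, or baseline.
- Other Table 5 rows: none sets grade 2 as its restart level. Allergic reaction needs grade 1 or less, liver tests baseline, renal function recovery to within 25% of baseline, heart failure resolution or baseline, and infection and gastrointestinal events resolution.

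The mismatch is therefore one CTCAE grade, in two rows. Text and table agree once baseline is reached.

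**Step 4: the time limit.** Table 5 starts to hold for neuropathy only after two weeks of persistence. If the 14 days in 10.2 ran from onset, the hold-and-restart step could not be reached. If they run from the start of withholding, it can.

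**Step 5: frequency.** Grade 3/4 neuropathy rates come from Protocol Sections 2.1.3.2 and 2.1.3.3:

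- carfilzomib with lenalidomide and dexamethasone, newly diagnosed (N = 53): grades 1/2 only, so 0%;
- carfilzomib with cyclophosphamide and dexamethasone (N = 58): grades 1 and 2 only, so 0%;
- PX-171-003-A1: 0.7%;
- carfilzomib, thalidomide and dexamethasone: 1% (polyneuropathy);
- PX-171-003-A0: 2.2%.

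Stated maximum number of patients (Section 19.1): 18 + 20 = 38. Expected cases = 38 × rate; chance of at least one = 1 − (1 − rate)^38.

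| Rate | Expected cases | Chance of at least one |
|---|---|---|
| 0% | 0 | 0 |
| 0.7% | 0.27 | 23% |
| 1% | 0.38 | 32% |
| 2.2% | 0.84 | 57% |

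The documents give no rate for painful grade 2 neuropathy, or for other carfilzomib-related events that settle at grade 2, so neither is sized.

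**The case against.** The best defence is that the exception is an obvious slip. Section 10.2 twice sends the reader to Tables 3 and 5 without any exception, Section 9.3.3 sends other toxicities to 10.4 and 10.5, and a literal reading leaves the neuropathy rows with little to govern. A clinician who opens Table 5 finds a direct instruction. This is plausible, but the text does not settle it, and it leaves both the instruction in 10.2 to delay for grade 3/4 toxicity and the restart mismatch in place.

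It can also be said that harm is limited. Section 9.3.3 lists peripheral neuropathy as very common with thalidomide, but does not list it among carfilzomib's commonest reactions. Section 10.7 covers thalidomide, Section 6.3.2 excludes severe functionally limiting neuropathy that may interfere with adherence, and Section 14.1.1 lets the investigator stop treatment for unacceptable toxicity. All of this stands and lowers the stakes. None of it says what to do with carfilzomib.

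Three stronger readings are tempting and are not supported:

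- **That these toxicities have no rule at all.** The general text still covers grades 3 and 4; the only complete gap is painful grade 2.
- **That every carfilzomib-related event settling at grade 2 is affected.** Only two Table 5 rows carry the mismatch.
- **That 10.2 sets two contradictory 14-day clocks.** The first statement names no starting point and follows directly on the withholding rules, so a single clock from withholding is a natural reading. It needs stating, not correcting.

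**Conclusion.** The inconsistency is real and concerns operative dosing rules: continue or withhold at grade 3 neuropathy, and restart or stop for an event that settles at grade 2 under the neuropathy or catch-all row. It is infrequent for grade 3/4 neuropathy, at 0 to about 0.8 expected patients among up to 38.

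That range assumes that the myeloma rates carry over, which is uncertain in both directions. The documents give no rate for AL amyloidosis, in which nerves may be involved. The 1% came from thalidomide 200 mg with twice-weekly carfilzomib, against 50 to 100 mg and weekly dosing here. The 2.2% came from a group of whom 78% had neuropathy at entry. The rates are not limited to sensory neuropathy, and applying them to all patients and cycles includes cycle 1 of escalation, which has its own rules.

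A reader might infer that the dose finding or the main analysis is compromised. The documents do not support that: DLTs are defined in Section 8.1.4, cycle 1 of escalation is handled in Section 10.1, and all analyses are descriptive. What is exposed is patient safety, plus the descriptive dose delays, reductions, withdrawals and relative dose intensity. The change should be made because it is cheap and removes a safety ambiguity.

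**What to change.** 1. Delete the exception in the closing sentence of Section 10.2. State in 10.2 and 10.5 that, outside cycle 1 of dose escalation, the Table 5 neuropathy rows prevail over the general grade 3/4 withholding and restart rules.
2. Change the restart level in the catch-all row of Table 5 to grade 1 or less, or baseline, to match 10.2 and 10.5. Letting the whole of Table 5 override the text would instead loosen the restart rule for every unlisted carfilzomib-related toxicity, which is a safety decision and not a clarification.
3. State that the 14-day discontinuation limit (three weeks for infection, as now) runs from the start of withholding, and that for neuropathy reaching the Table 5 restart threshold counts as resolved.

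The cost is one deleted clause, one changed table entry and two or three sentences in a single amendment, plus notice to sites. No extra patients, visits or tests are needed. The documents do not show which threshold was intended, so the Chief Investigator should confirm items 1 and 2. Under item 2, some patients who could restart at grade 2 under the present table would wait longer or stop.
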